9.2 Sample Size and Randomization

Based on our past trials, we project 95% retention at 4-weeks. We estimated standard deviations of each outcome based on patients in a similar project with analogous eligibility criteria, and conservatively estimated pre-post correlations to be 4%-7% smaller than the values in this study. Assuming a sample size of 316, of which 280 meet all eligibility criteria and 92% of enrolled participants are retained to 4 weeks, the table below displays minimum detectable effect sizes for a) main effects of each protocol component, b) pairwise interactions between components, c) comparison of mean outcome between two levels of one component at a fixed level of another component, d) main effects of the 3 components in subgroup analyses involving half the participants, and e) pairwise interactions between 2 components in subgroup analyses with half the participants. This sample size provides at least 80% power to detect the MCID or hypothesized effect sizes for the main effects of each component for all outcomes, and for analyses of main effects in subgroups and conditional comparisons for each outcome except global stiffness. Power is more limited for secondary aims, such as pairwise interactions within subgroups.

	Assumptions for Outcome Measures in Project			
	Global Stiffness (N)	Multifidus Activation (mm)	Oswestry	Numeric Pain Rating
Assumption				
Mean (SD)	5.55 (1.60)	2.60 (0.124)	24.3 (14.9)	5.06 (2.12)
Pre-post score correlation	0.80	0.70	0.70	0.45
MCID or hypothesized effect size from past work	0.40	0.074	6.0	2.0
Type of effect	Detectable Effect Size			
Main effect	0.37	0.034	4.12	0.76
Pairwise interaction	0.74	0.064	8.24	1.53
Conditional comparison	0.53	0.045	5.83	1.08
Main effect in 50% of subjects	0.53	0.045	5.83	1.08
Interaction in 50% of subjects	1.05	0.091	11.65	2.16

Table. Assumptions and detectable effect sizes informing sample size for the project.

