Adjusted means with CIs will be provided for each treatment combination. Interaction plots will be used to depict significant interactions and linear contrasts constructed to evaluate the effect of each intervention conditional on the presence or absence of the other intervention. To account for 2 primary outcomes, each of the hypothesis tests noted above will be performed with 2-sided $\alpha=0.025$ and confidence intervals will be constructed using a confidence coefficient of 0.975. The indicated comparisons at 4-weeks will be given primary emphasis in evaluating the effects of each intervention. Comparisons at 3-months will evaluate persistence of effects following intervention.

Primary Aim #2: The OSW and NPRS will be co-primary outcomes for evaluating the effects of the 3 SMT protocol components on patient centered outcomes. The same analytic approach described above will be used. To account for 2 outcomes, we will again apply a 2-sided $\alpha=0.05$ and 97.5% CIs for statistical inference.

Secondary Aim #1: It is unknown how early SMT response may affect response to additional intervention. We will examine this question by evaluating responder status after 1 week as a possible effect moderator by adding a main effect for responder status and interaction terms between responder status and the indicator variables for treatments (and treatment combinations) which are retrained in the final simplified models for the different outcomes developed using the BIC criteria for each of the co-primary outcomes for the primary aims 1 and 2. Statistically significant interactions between responder status and main effect and/or interaction terms between treatment intervention components will be interpreted as suggesting effect moderation. Recognizing that tests for interactions have limited statistical power, we will also fit the simplified models developed in Aims 1 and 2 separately under the presence and absence of each factor (dichotomizing using a median split for continuous factors), and graphically display the estimated treatment effects at both levels of responder status. Recognizing the potential for lower statistical power, the results of Secondary Aim #1 will be interpreted as exploratory.

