Secondary Aim #2: In order to assess which intervention component combinations provide optimal outcomes, we will first simplify the fully saturated factorial analysis of variance model by comparing the Bayes Information Criterion (BIC) among all possible models including different combinations of main effects, pairwise interactions and the 3-way interaction which satisfy the hierarchical consistency constraint that the main effects corresponding to each term in a pairwise interaction are retained in models with pairwise interactions, and all component main effects and pairwise interactions are retained when considering the 3-way interaction. This will result in a more parsimonious model to increase statistical power. Then, using the simplified model, for each outcome we will use a simulation approach to derive simultaneous 97.5% CIs for all comparisons of estimated mean outcome under each possible treatment combinations (No further treatment, A, B, C, AxB, AxC, BxC, AxBxC). After ordering the treatment combinations in accordance with the observed mean outcome, the simultaneous CIs will be used to identify which combinations are statistically indistinguishable from the optimum treatment, thus identifying a set of candidate options for the best combination of treatments. This process will be applied for both mechanistic and patient-centered outcomes. We anticipate that more than one combination will be considered optimal for different outcomes, and that the combinations that are optimal will differ for different outcome measures. Our interpretation of optimized protocols will give preference to longer term outcomes (ie, 3-month scores) and patient-centered outcomes. We will also consider an application of the robust modelling approach to derive a model for the optimum combination of components as a multivariate function which jointly incorporates each the potential effect modification of week 1 responder status in the same model. This approach will estimate the combination of components providing the optimum expected outcome for each participant based on their responder status after 1 week.

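### Secondary Aim #2: the simultaneous 97.5% intervals that pick the candidate protocols come from a BIC-selected model with no stated allowance for the selection, so they do not have the stated level

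*Combined protocol and SAP*

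**What the plan says.** Section 9.6, under Secondary Aim #2, sets out a sequence of steps.

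- **Selection.** The saturated factorial model is reduced by "comparing the Bayes Information Criterion (BIC) among all possible models including different combinations of main effects, pairwise interactions and the 3-way interaction", subject to the rule that lower-order terms stay in whenever a higher-order term is in. The reason given is: "This will result in a more parsimonious model to increase statistical power".
- **Intervals.** "Then, using the simplified model, for each outcome we will use a simulation approach to derive simultaneous 97.5% CIs for all comparisons". The simulation approach is not described further.
- **Decision.** The combinations are ranked by observed mean, and "the simultaneous CIs will be used to identify which combinations are statistically indistinguishable from the optimum treatment". The result is the list of candidate optimized protocols.

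The 97.5% level matches Primary Aim 1, where "confidence intervals will be constructed using a confidence coefficient of 0.975" to allow for two co-primary outcomes. Nothing in section 9 says that the simulation repeats the BIC step, averages over models, splits the data or goes back to the full model. Secondary Aim #1 is called exploratory. Secondary Aim #2 is not.

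**The concern.** The same data choose the model and then supply the intervals, and the text treats the chosen model as given. Two things follow.

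- If a component and its interactions are dropped, the fitted means with and without it are identical. The interval for that comparison is the single point 0, which misses any true effect other than exactly zero.
- If a term is kept because its estimate happened to be large, its interval takes no account of that.

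These intervals decide which protocols go forward. Section 2.2 presents the optimized protocols as the trial's product, ready for later randomized trials. A level that the intervals do not have would be attached to that product.

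**Working it through.** **Inputs.** Section 9.2 gives an Oswestry SD of 14.9, a pre-post correlation of 0.70, a hypothesized effect (MCID) of 6.0, a detectable main effect of 4.12, and 316 recruited, "of which 280 meet all eligibility criteria and 92% of enrolled participants are retained to 4 weeks". Allocation is equal over 8 combinations (Précis).

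**Plan's own figure.**
- Analysed N = 280 × 0.92 = 257.6.
- Residual SD = 14.9 × √(1 − 0.70²) = 10.64.
- Detectable main effect at 80% power and two-sided alpha 0.025 = (2.241 + 0.842) × 10.64 × 2/√257.6 = 4.09, against 4.12 stated. Alpha 0.05 gives 3.71, so the table was built on 0.025, although the Aim 2 text mentions 0.05.

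**Number of models.** Models that respect the hierarchy rule: 1 with no terms; 3 with one main effect; 3 × 2 = 6 with two main effects, with or without their interaction; 2³ + 1 = 9 with all three main effects. The total is 19.

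**What BIC keeps.** With one parameter per term, a term survives if |z| > √ln 258 = 2.36 (p about 0.018). The standard error of a main effect is 2 × 10.64/√258 = 1.325, so the threshold is 2.36 × 1.325 = about 3.1 points. The chance that a single term is dropped is P(Z < 2.36 − effect/1.325):
- 3 points: 54%
- 4.12 points: 23%
- 6 points: 1.5%

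**Simulation.** Assumptions: one follow-up visit analysed by ANCOVA, equal cells, normal errors, and BIC choice among the 19 models. Simultaneous 97.5% intervals for all 28 differences use the simulated maximum-|t| critical value of the selected model, treated as fixed. There were 8,000 to 20,000 trials per scenario. Main effects are averaged over the other components; an interaction is a difference of differences. Repeat runs differed by up to about 2 percentage points in coverage and 0.1 in set size.

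| True effects (Oswestry points) | Coverage, BIC-selected | Mean candidate set of 8: selected / full model |
|---|---|---|
| None | 94% | 7.8 / 8.0 |
| A = 6 | 94% | 4.0 / 6.5 |
| A = B = C = 6 | 93% | 1.25 / 3.9 |
| A = 4.12 | 74% | 4.9 / 7.5 |
| A = B = C = 4.12 | 47% | 2.5 / 5.6 |
| A = 6, B = 3 | 45% | 3.3 / 5.9 |
| A = B = 6, antagonism 6 | 50% | not tabulated |
| A = 6, B = 2, antagonism 6 | 27% | 4.35 / 6.3 |
| A = B = C = 3 | 10% | 4.2 / 6.8 |

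Intervals from the full model covered at about 97% in every scenario.

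**Where the failures come from.** At least one zero-width interval appeared in nearly every trial when some component had no effect, in 53% with all three at 4.12, and in about 5% with all three at 6. There are also false separations. With all three at 4.12, some pair of truly equal combinations was declared different in 51% of trials, because one of two equal components was kept and the other dropped.

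**Does the set keep a best combination?** It did in at least 99.7% of trials in the additive scenarios. It did in 93.5% with A = 6, B = 2 and antagonism 6, and in 89% to 98% across several scenarios with a missed antagonism. The full model gave 100%.

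**Sensitivity to the BIC count.** If each term counts as two parameters (4 weeks and 3 months), coverage with no effects rises to 99.7%. It falls to 39% for A = 4.12 alone and to 67% for all three at 6. The plan does not say which count applies.

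**The case against.** The case on the other side has real weight.

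- **A reader might infer that coverage is always far below 97.5%.** The plan's own figures do not support that. With the one-visit count, coverage is 93-95% if additive effects are zero or at the hypothesized 6 points. The 10% figure needs three effects of half the MCID, where a false tie matters less.
- **A reader might infer that components of the planned size are often dropped.** The 4.12 points are the detectable effect; the hypothesized effect is 6.0, and a 6-point term is dropped in about 1.5% of trials. The 23% drop rate at 4.12 is close to the 20% miss rate that 80% power already accepts. But a missed test still leaves an interval with width, and a dropped term does not.
- **A reader might infer that the procedure loses the best protocol.** A dropped component leaves both versions in the set, so in additive settings a best combination almost always stays. Where an antagonism is missed, the loss can be small: with A = 6, B = 2 and antagonism 6, adding B to A changes the outcome by 2 − 6/2 = −1, so the retained rival is 1 point worse.
- **A reader might infer that equal combinations are separated too often when nothing works.** The one-visit count gives about 6% against 2.5%, but the two-parameter count reverses this.
- **The simulation approach is undefined.** It could repeat the selection. The text does not say so, and its natural reading is that the chosen model is fixed.
- **Parsimony is deliberate, and full-model results are already planned.** Aims 1 and 2 report all main effects and interactions, and adjusted means with intervals for each combination, before any BIC step. The primary inference is therefore untouched.

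These points limit the size and importance of the problem. They do not give a zero-width interval 97.5% coverage, and joint coverage of all comparisons is what the plan claims.

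**Conclusion.** The point holds, with its size conditional on the true effects. As written, the simultaneous intervals for Secondary Aim #2 do not have the stated 97.5% level. The shortfall is mild (93-95%) for additive effects that are zero or at 6 points. It is material when a component has a real effect near or below the 4.12-point detectable size, or when a moderate interaction is missed: about 74%, 50%, 47%, 45% and 10% in the scenarios shown. The consequences are false ties between combinations a few points apart, candidate sets narrower than the stated level supports, and occasional loss of the best combination under antagonism.

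The exact percentages rest on the Oswestry planning values, a single visit and one BIC parameter per term; the zero-width intervals do not. This should be corrected before analysis. It does not undermine the primary aims, and the documents do not support saying that the candidate set will generally miss the best protocol.

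**What to change.** In section 9.6, Secondary Aim #2, derive the simultaneous 97.5% intervals and the candidate set from the saturated factorial model already fitted for Aims 1 and 2. Describe the simulation that gives the critical value. Report the BIC-simplified set beside it as descriptive, labelled as conditional on the selected model, with no 97.5% level and no zero-width intervals.

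Building the BIC step into the simulation or bootstrap, or averaging over models, would also address the selection, but would need fuller specification and a check of coverage.

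The change is to wording only. The statistical cost is real:
- The Oswestry half-width for two combinations becomes about 3.26 × 10.64 × √(2/32.25) = 8.6 points, where 32.25 = 258/8 per cell.
- Candidate sets grow, for example to about 5.9 from 3.3 of 8 when A = 6 and B = 3.
- With a single 4.12-point component, the chance of separating any two combinations falls from 78% to 36%. The higher figure came from intervals that covered in only about 74% of trials.

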9.6 Data Analyses

Primary Aim 1: Spine stiffness and multifidus activation will be co-primary outcomes for evaluating effects of SMT protocol components on SMT mechanisms. The effect of intervention components (A additional SMT; B multifidus activation; C mobilizing exercises) on each outcome will be evaluated using linear mixed models to relate mean levels of each outcome at 1-, 4-weeks and 3-months to indicator variables to represent the main effects of each interventions (A, B, C) as well as each pairwise interaction between the interventions (AxB, AxC, BxC) and the 3-way interaction (AxBxC). 1-week assessment, which occurs just before randomization, will serve as the baseline for these analyses and the model will be assumed equal between the randomized groups. This model, sometimes referred to as a constrained longitudinal model, leads to adjustment for baseline levels as in analysis of covariance (ANCOVA), which has been shown to remove conditional bias in treatment group comparisons due to chance imbalances and improve statistical power over unadjusted comparisons. An unstructured covariance matrix will be used to account for correlation of serially measured outcome scores in the same subject. By using an unstructured covariance matrix, the model will constitute a special case of a general linear mixed model which avoids imposing specific assumptions concerning distribution of random effects. This modelling approach is recommended in randomized trials when the number of follow-up outcome assessments is small. Restricted maximum likelihood estimation will be used for estimation of parameters and their associated standard errors.

Linear mixed effects analysis will provide estimates and CIs for the following quantities for each outcome at both 4-week and 3-month assessments: a) Main effects evaluating effects of each of the 3 interventions while averaging over the levels of the other 2 interventions. b) Three pairwise interactions evaluating if the effect of an intervention differs between levels of another interventions, while averaging over levels of the 3rd intervention. Pairwise interactions will inform whether the effects of each intervention pair are additive, synergistic or antagonistic. c) 3-way interaction evaluating if each pairwise interaction differs depending on the 3rd intervention.

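### Secondary Aim #2 picks the reference optimum by an undefined observed mean but tests against it with simplified-model means; read literally, the reference can be a combination the plan's own intervals call inferior

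*Combined protocol and SAP*

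**What the plan says.** The procedure for Secondary Aim #2 is in Section 9.6. The saturated factorial model is first reduced by BIC over all hierarchical models. From the reduced model, and separately for each outcome, simulation then serves to "derive simultaneous 97.5% CIs for all comparisons of estimated mean outcome under each possible treatment combinations". The sentence after that sets the reference: "After ordering the treatment combinations in accordance with the observed mean outcome, the simultaneous CIs will be used to identify which combinations" belong with the one ranked first. The combinations kept are described as "statistically indistinguishable from the optimum treatment, thus identifying a set of candidate options for the best combination of treatments".

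The model behind the intervals is described under Primary Aim 1 in the same section. It is a constrained longitudinal model with the 1-week value as baseline, which adjusts for that value as ANCOVA does. Under that aim the plan also promises cell-level results: "Adjusted means with CIs will be provided for each treatment combination". Nothing says that these adjusted means, or the simplified-model means, are the ones used for the ordering. No rule covers the case where the two orderings disagree.

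**The concern.** The candidate set is defined relative to whichever combination is ranked first. If the ranking uses raw cell means and the intervals use simplified-model means, the two can disagree for two reasons. Raw means keep chance imbalance in the 1-week value, which the model removes. Raw means also rest on one cell each, whereas a simplified model that has dropped interactions estimates each combination from the whole sample.

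When they disagree strongly enough, the reference is significantly worse than another combination by the plan's own intervals. That other combination is then distinguishable from the so-called optimum, so the literal rule removes it although it is better. Secondary Objective II (Section 1.2) is to define the optimized protocols, and Section 2.2 intends them for future trials. This step feeds that deliverable.

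**Working it through.** **Inputs.** Section 9.2: 280 enrolled and 92% retained at 4 weeks, so 280 × 0.92 = 257.6, or about 32 in each of 8 equal cells. SD and pre-post correlation are 14.9 and 0.70 for Oswestry, 1.60 and 0.80 for global stiffness, 2.12 and 0.45 for pain, 0.124 and 0.70 for multifidus activation. Section 9.6: 97.5% intervals.

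**The plan's own figure.** The adjusted Oswestry SD is 14.9 × √(1 − 0.70²) = 10.64. The detectable main effect at two-sided 0.025 and 80% power is (2.241 + 0.842) × 2 × 10.64 / √257.6 = 4.09 (4.11 with t quantiles), against 4.12 in the table. Alpha 0.05 gives 3.71 and does not reproduce it. The documents give no figure for the ranking step.

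**Why the orderings differ.** For Oswestry with 32 per cell:
- SE of a raw difference between two cells: 14.9 × √(2/32) = 3.73.
- SE of one component's effect in an additive adjusted model: 2 × 10.64 / √256 = 1.33. The simultaneous 97.5% critical value for that model is about 2.965, so a difference above 2.965 × 1.33 = 3.94 is declared.
- If three components are each worth 4.12 points, one given two-component combination beats the best one on raw means with probability Φ(−4.12/3.73) = Φ(−1.11), about 13%. There are three such rivals. The model can meanwhile declare a difference of that size.
- The variance ratio from baseline adjustment alone, 1/(1 − r²), is 1.96 at r = 0.70, 2.78 at 0.80 and 1.25 at 0.45. Stiffness is therefore worst affected and pain less so.

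**Simulation of the stated procedure.** 32 per cell, normal complete data, ANCOVA standing in for the longitudinal model, BIC over the 19 hierarchical models, simulated max-|t| 97.5% intervals. True effects are assumed. Separate runs used 2,000 to 20,000 trials per scenario; ranges are across runs.

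| True effects | Raw-mean reference called inferior |
|---|---|
| Oswestry, none | 0.1–0.4% |
| Oswestry, one of 6 | 0.8–1.5% |
| Oswestry, one of 4.12 | 2.2% |
| Oswestry, two of 6 | 3.6–4.2% |
| Oswestry, two of 4.12 | 5.6% |
| Oswestry, three of 4.12 or of 6 | about 8–10% |
| Global stiffness, three of 0.40 | 14–15% |
| Pain, three of 0.76 | 3.6–3.8% |
| Pain, three of 2.0 | 0.02–0.03% |
| Multifidus, three of 0.074 | 1.9% |

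With three active components, essentially all of these trials lose the truly best combination from the candidate set. With antagonistic Oswestry components this is less so: for effects of 6 and 4 with interaction −4, the reference is called inferior in 5.1% and the best is lost in 2.1%; for 6 and 6 with interaction −6, the figures are 5.6% and 0%.

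**After the change.** If the ranking uses the simplified-model means that the intervals compare, the reference cannot be called inferior. The best combination was wholly lost in 0.0% of trials in every scenario run.

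**The case against.** The strongest reply is that the ordering term appears once and is undefined. In work on selecting the best treatment, observed often means the sample estimate as opposed to the true mean. The sentence follows directly from the simplified-model intervals, and the only cell means that Section 9.6 promises are adjusted. On the simplified-model reading the problem is zero; on a saturated-model adjusted reading it is 0–2%. This stands as a possible reading. It does not settle the matter, because consecutive sentences use estimated and observed without equating them, and an analyst could properly follow the literal text.

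The size is also open to challenge, and most of this stands:
- The 8–10% needs all three components to work, while Section 2.2 allows that some may be discarded.
- Randomization is stratified by responder status, which is computed from the 1-week Oswestry, the model's baseline. If responder status explains 30–45% of that score's variance and the strata balance well (assumptions), the three-component Oswestry rate is about 5–7%.
- Section 9.6 prefers 3-month outcomes, and no 3-month correlation is given. At an assumed 0.50 or 0.30 the rate is about 3–4% or 2%.
- Intervals are planned for all comparisons, so a careful analyst could notice the contradiction. The plan does not say what to do then.

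A reader might infer that the plan certainly ranks on raw means, or that about one trial in ten would go wrong whatever the truth. The documents support neither: the term is undefined, and the rate ranges from almost nothing to about 15%. A reader might also quote top-rank accuracy for Oswestry with three components of 4.12 (about 71% on raw means, 86% on full-model adjusted means) as the gain from the fix. It is not, because the full model does not supply the intervals and the plan reports a set. Nor can missing data be counted here: none was simulated, and Section 9.2 expects little at 4 weeks.

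**Conclusion.** The point holds as a mismatch in the wording of the selection rule. Its consequence is real under the literal reading and absent under the simplified-model reading. The material figures are about 8–10% for Oswestry with three active components and about 15% for global stiffness; with one active Oswestry component or none the risk is small. These rest on assumed true effects, complete balanced normal data, 4-week SDs and correlations, and no modelling of stratification. Only Secondary Aim #2 is affected. The change is still worth making, because the literal rule can remove the best combination from the result this aim exists to produce.

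**What to change.** In Section 9.6, Secondary Aim #2, replace observed mean outcome by: mean outcome estimated from the same simplified model, outcome and visit that supply the simultaneous CIs. Add that combinations with equal estimated means are treated as joint optimum, since a simplified model that drops a component gives exact ties. State that raw cell means are shown for description only. The cost is one phrase and two short sentences. No extra data or analysis is needed, and the primary analyses do not change. If the simplified-model estimate was always intended, the same edit removes the ambiguity.

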We will recruit a total of 316 subjects age 18-60 with non-specific LBP and an Oswestry Disability score of at least 20%. Following Phase I treatment, subjects will be randomized in equal proportions to one of 8 possible treatment combinations in Phase II. Randomization will be stratified by responder status (yes/no) during Phase I.

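### Secondary Aim #2 selects the candidate best combinations with all-pairs intervals, although comparisons with the best would suffice; the loss is modest after the BIC step, and the change is optional and cheap

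*Combined protocol and SAP*

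**What the plan says.** Secondary Aim #2 in Section 9.6 sets out a sequence of steps.

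- The plan will "simplify the fully saturated factorial analysis of variance model by comparing the Bayes Information Criterion (BIC) among all possible models", subject to a hierarchy constraint.
- From the simplified model it derives by simulation, for each outcome, "simultaneous 97.5% CIs for all comparisons of estimated mean outcome under each possible treatment combinations". The eight combinations are listed, so the family has 8 × 7 / 2 = 28 pairs.
- It orders the combinations by observed mean and states that "the simultaneous CIs will be used to identify which combinations are statistically indistinguishable from the optimum treatment". Those that cannot be told apart from the optimum become the candidates for the best one.

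Section 9.6 names no other use for the pairwise intervals and no method restricted to comparisons with the best. The Précis says participants are "randomized in equal proportions to one of 8 possible treatment combinations in Phase II". The documents give no critical value, interval width or expected size of the candidate set for this aim.

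**The concern.** The intervals protect 28 statements, but the rule reads only the comparisons with the optimum. A procedure calibrated to those comparisons can keep the true best with 97.5% probability using a smaller critical value. Wider intervals leave more combinations indistinguishable from the best.

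Narrowing the field is the purpose of this aim: Section 1.2 sets out to define optimized protocols, and Section 2.2 expects them to feed later trials. The plan also simplifies the model expressly to gain power at this step. An over-wide error family gives part of that gain back and may carry inferior multi-component protocols forward.

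**Working it through.** **Inputs.** Section 9.2: "Assuming a sample size of 316, of which 280 meet all eligibility criteria and 92% of enrolled participants are retained to 4 weeks"; Oswestry SD 14.9; "Pre-post score correlation" 0.70. The same section also states that "we project 95% retention at 4-weeks"; I use 92%, the figure tied to the detectable-effect table. Section 9.5.1: Oswestry MCID 6 points. Section 9.6: 97.5% intervals.

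- Analysed: 280 × 0.92 = 257.6, or 257.6 / 8 = 32.2 per combination.
- Adjusted SD: 14.9 × √(1 − 0.70²) = 10.64.

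**The plan's own figure.** Detectable Oswestry main effect at two-sided 0.025 and 80% power: (2.241 + 0.842) × 2 × 10.64 / √257.6 = 4.09, or 4.11 with the t distribution; the table prints 4.12. At two-sided 0.05 it would be about 3.71. The inputs and the 97.5% level are therefore those behind the table.

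**Critical values, saturated model, large degrees of freedom.**

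- All pairs: 97.5% studentized range for 8 means divided by √2 = 3.26.
- MCB: one-sided 97.5% Dunnett constant, 7 comparisons, correlation 0.5 = 2.61.
- Standard error of a difference: 10.64 × √(2/32.2) = 2.652. Half-widths: 3.256 × 2.652 = 8.63 and 2.613 × 2.652 = 6.93 points, so MCB is 20% narrower.
- With all means equal, a given best combination is kept with probability about 0.996 under all pairs, against the 0.975 target, and 0.975 under MCB.

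**Critical values after BIC.** There are 19 hierarchical models. In the 18 non-empty ones, including the saturated model, the MCB value is 12% to 20% smaller. Examples: additive three-component model 2.94 against 2.55; one-component model 2.24 against 1.96. In a one-component model the two rules coincide, because BIC retains a component only if z² > ln(257.6) = 5.55, that is |z| > 2.36, which exceeds both values.

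**Average number of combinations kept.** Simulated trials, residual SD treated as known, Oswestry scale. The true effects are assumptions, set at 4.12 and 6 points.

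| True main effects | After BIC: all pairs | After BIC: MCB | Trials where the set changes | Saturated: all pairs | Saturated: MCB |
|---|---|---|---|---|---|
| 6, one component | 4.03 | 3.99 | 2% | 6.5 | 5.3 |
| 6, two components | 2.15 | 2.08 | 4% | 5.0 | 3.9 |
| 6, three components | 1.23 | 1.12 | 10% | 3.8 | 3.0 |
| 4.12, three components | 2.47 | 2.00 | 31% to 32% | 5.5 | 4.4 |

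In the first row four combinations are truly tied for best, and in the second row two are. With no true effect, the two rules give the same set after BIC in 99.9% of trials.

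**Retention of the best after BIC.** The intervals take the BIC-chosen model as known. Assume 6A + 6B − 6AB in 0/1 indicators: A (additional SMT) or B (multifidus exercise) gives 6 points, both together still give 6, and C (mobilizing exercise) gives nothing. Six combinations tie for best. The interaction has expected z = 6 / 2.652 = 2.26, below the BIC threshold of 2.36, so it is often dropped, and an additive model then makes A with B look better than either alone. A combination containing only one of A and B is kept about 72% of the time with all pairs and 69% with MCB. With the saturated model the figures are about 99.7% and 98%.

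**The case against.** The strongest reply is that the plan is valid as written. All-pairs simultaneous intervals are a standard, conservative choice, and conservatism protects the best combination. They also give joint coverage for differences among the retained combinations, which has some use because the plan expects several candidates and will weigh them across outcomes. That stands: MCB gives up this coverage.

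A reader might infer from the saturated-model columns that about one combination fewer would be kept (6.5 to 5.3, 5.0 to 3.9, 3.8 to 3.0). The documents do not support that, because the intervals come from the BIC-simplified model. After that step the three 6-point scenarios change by 0.04, 0.07 and 0.11.

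A reader might also infer that MCB has no downside and keeps the true best at least 97.5% of the time. Within this plan it does not: the intervals ignore the model selection, and in the antagonistic pattern MCB lowers retention that is already short. All pairs does not repair this either, so it is a reason to deal with selection rather than to keep the wider family.

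What remains is a real but modest loss, largest among the scenarios examined when every component has about the effect the trial was sized to detect.

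**Conclusion.** The point holds as an efficiency matter confined to Secondary Aim #2. The selection is more conservative than its purpose requires, but no analysis is invalid and the primary aims are untouched. On the Oswestry scale after BIC, MCB would remove about half a combination on average if each component is worth 4.12 points, and about a tenth of one or less in the 6-point scenarios.

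These figures assume equal cells of 32.2, an adjusted SD of 10.64, the Section 9.2 correlation applied to the 1-week baseline, and the stated true effects. They use the 4-week retention figure, while the plan gives preference to 3-month scores when interpreting the optimum. An optional, cheap improvement.

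**What to change.** In Secondary Aim #2, replace the all-pairs intervals with simulation-based MCB intervals at 97.5%, using the covariance of the eight estimated means. Keep a combination when no other combination exceeds it by more than the MCB margin, and report the remaining pairwise differences descriptively.

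In the same edit, either base the intervals on the saturated model or have the simulation repeat the BIC selection in each draw. If the second route is taken, report retention of the best under main-effect and antagonistic-interaction patterns, so that the 97.5% claim is checked.

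Costs: a few sentences of SAP text, a different maximum statistic and slightly more simulation work, and loss of joint coverage among the retained combinations. The saturated route also gives larger sets: with 4.12 points per component, MCB would keep about 4.4 combinations, against about 2.5 under the present BIC and all-pairs plan. No data collection or sample size changes.
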